5.3.5.3. Treatment after Initial Evidence of Radiological Disease Progression

Immunotherapeutic agents such as avelumab and the other immune modulators to be evaluated in this study may produce antitumor effects by potentiating endogenous cancer-specific immune responses. The response patterns seen with such an approach may extend beyond the typical time course of responses seen with cytotoxic agents, and can manifest as a clinical response after an initial increase in tumor burden or even the appearance of new lesions.

If radiologic imaging shows disease progression, tumor assessment should be repeated ≥ 4 weeks later in order to confirm the observation. Assigned study treatments may be continued at the Investigator's discretion while awaiting radiologic confirmation of disease progression.

Patients may receive study treatments while waiting for confirmation of PD if they are clinically stable as defined by the following criteria:

- Absence of clinical signs and symptoms (including worsening of laboratory values) of disease progression.
- No decline in ECOG performance status.
- Absence of rapid progression of disease by radiographic imaging.
- Absence of progressive tumor at critical anatomical sites (eg, cord compression) requiring urgent alternative medical intervention.

If repeat imaging no longer shows PD but rather CR, PR or SD compared to the initial scan, treatment may be continued/resumed. In determining whether or not the tumor burden has increased or decreased, Investigators should consider all target as well as non-target lesions (refer to the Study Manual). Before continuation of treatment after initial PD, the patient must be re-consented via an informed consent addendum and informed that by continuing to receive investigational products, the patient may be foregoing available therapy with possible clinical benefit(s).

If repeat imaging does not confirm PD, treatment with investigational products may be continued.

If the repeat imaging confirms PD, patients should be considered for discontinuation from all investigational products. However, according to the Investigator's clinical judgment and after discussion between the Investigator and the Sponsor, if a patient with evidence of PD is still experiencing clinical benefit, the patient may be eligible for continued treatment with the investigational products. The Investigator's judgment should be based on the overall benefit-risk assessment and the patient's clinical condition, including performance status, clinical symptoms, adverse events, and laboratory data.

Patients who stop treatment for reasons other than toxicity with any of the investigational products and then experience radiologic disease progression shortly thereafter will be eligible for re-treatment with the investigational products at the discretion of the Investigator and after discussion with the Sponsor.

5.3.5.4. Treatment after Confirmed Complete Response

Patients who have experienced a confirmed CR may continue treatment under the discretion of the investigator and upon agreement with the Sponsor for up to 2 years from the first dose of investigational product (Cycle 1 Day 1).

5.3.6. Food Requirements

The IV, SC, and IT investigational products may be administered without regard to food.

5.3.7. Recommended Dose Modifications

Every effort should be made to administer each of the investigational products at the planned dose and schedule. No dose modifications are permitted in this study, but the next administration of investigational product may be omitted based on persisting toxicity, as outlined in the next sections.

5.3.7.1. Dose Delays

In the event of significant toxicity, dosing for investigational products may be delayed as described below. In the event of multiple toxicities, dose delays should be based on the worst toxicity observed. Patients are to be instructed to notify Investigators at the first occurrence of any adverse symptom. In addition to dose delays, investigators are encouraged to employ best supportive care according to local institutional clinical practices and according to the guidance for selected adverse events provided below.

5.3.7.2. Study Treatment Modifications for Investigational Products Drug-Related Toxicity

Recommended treatment modifications for the investigational product attributable to drug-related toxicity are shown in Table 21.

Table 21. Avelumab, Utomilumab, PF-04518600, PD 0360324, and CMP-001 Treatment Modifications for Drug-Related Toxicity

Toxicity	NCI CTCAE Severity Grade	Treatment Modification
Drug-related adverse reactions (excluding infusion-related reaction/hypersensitivity and immune-related AEs)	Grade 1	
Continue per schedule.
	Grade 2	
Continue per schedule.Consider withholding treatment for intolerable adverse reaction based on medical judgment.
	Grade 3	
Withhold until recovery to Grade 1 or better.If toxicity does not resolve to Grade 1 or better within 12 weeks of last administration or if based on medical judgment the event is considered critical, consider permanent discontinuation after consultation with the sponsor.Upon the second occurrence of the same Grade 3 toxicity that does not resolve to Grade ≤1 by the next administration, treatment must be permanently discontinued. 
Exceptions are: Laboratory values out of normal range that do not have any clinical correlation.

	Grade 4	
Permanent discontinuation. 
Exceptions are: Laboratory values out of normal range that do not have any clinical correlation.

Infusion-related Reaction	Grade 1-4	
See Section 5.3.7.3.1 and Table 22.
Hypersensitivity reactions	Grade 3-4	
See Section 5.3.7.3.2.
Immune-related AE (irAE)	Grade 1-4	
See Section 5.3.7.3.4 and Table 25.

5.3.7.3. Special Precautions for Avelumab, Utomilumab, PF-04518600, PD 0360324, and CMP-001 Administration

As with all monoclonal antibody therapies, there is a risk of allergic reactions including anaphylactic shock. Investigational products (biologics) should be administered in a setting that allows for immediate access to an intensive care unit or equivalent environment and administration of therapy for anaphylaxis, such as the ability to implement immediate resuscitation measures. Steroids (dexamethasone 10 mg), epinephrine (1:1,000 dilution), allergy medications (IV antihistamines), bronchodilators, or equivalents, and oxygen should be available for immediate access.

Premedications to mitigate infusion-related reactions associated with investigational product administration are described in [Section 5.3.5](#).

Treatment recommendations for the management of infusion-related reactions, severe hypersensitivity reactions, and CRS are outlined in [Section 5.3.7.3.1](#), [Section 5.3.7.3.2](#) and [Section 5.3.7.3.3](#), respectively.

Investigators should also monitor patients closely for potential irAEs, which may become manifest at the earliest after weeks of treatment. Such events may consist of persistent rash, diarrhea and colitis, autoimmune hepatitis, arthritis, glomerulonephritis, cardiomyopathy, or uveitis and other inflammatory eye conditions. The spectrum of hypothetical irAEs also includes formation of auto-antibodies like antinuclear antibodies (ANAs) or antineutrophil cytoplasmic antibodies (ANCAs). Treatment recommendations for the management of irAEs are outlined in [Section 5.3.7.3.4](#).

5.3.7.3.1. Management of Infusion-Related Reactions

Since some of the investigational products (mAbs) are administered IV, infusion-related reactions may occur (with symptoms such as fever, chills, rigors, diaphoresis, and headache). Treatment of the infusion-related reaction and modifications of the infusion(s) are mainly dependent upon severity, as indicated in Table 22.

Table 22. Treatment Modification for Symptoms of Infusion-Related Reactions

NCI CTCAE Grade	Treatment Modifications
Grade 1 – mild Mild transient reaction; infusion interruption not indicated; intervention not indicated.	Decrease the investigational product infusion rate by 50% and monitor closely for any worsening. ^a
Grade 2 – moderate Therapy or infusion interruption indicated but responds promptly to symptomatic treatment (eg, antihistamines, NSAIDs, narcotics, IV fluids); prophylactic medications indicated for ≤24 hours.	Stop investigational product infusion. Resume infusion at 50% of previous rate as soon as infusion-related reaction has resolved or decreased to at least Grade 1 in severity, and monitor closely for any recurrence or worsening. ^a
Grade 3 or Grade 4 – severe or life-threatening Grade 3: Prolonged (eg, not rapidly responsive to symptomatic medication and/or brief interruption of infusion); recurrence of symptoms following initial improvement; hospitalization indicated for clinical sequelae. Grade 4: Life-threatening consequences; urgent intervention indicated.	Stop the investigational product infusion immediately and disconnect bag infusion tubing from the patient. Investigational product treatment must be permanently discontinued.

IV=intravenous, NCI-CTCAE=National Cancer Institute Common Terminology Criteria for Adverse Event, NSAIDs=nonsteroidal anti-inflammatory drugs.

a. The total infusion time for each investigational product should not exceed 120 minutes.

Once the investigational product infusion rate has been decreased by 50% due to an infusion-related reaction, it must remain so for the next scheduled infusion. If no infusion reaction is observed at the next scheduled infusion, the infusion rate may be returned to baseline at subsequent infusions.

Additional Modifications for Patients with Grade 2 Infusion-Related Reactions: In the event of a Grade 2 infusion-related reaction that does not improve or worsens after implementation of the modifications indicated in Table 22 (including reducing the infusion rate by 50%), the Investigator may consider treatment with corticosteroids, and the infusion should not be resumed for that infusion. At the next infusion, the Investigator may consider

the addition of H2-blocker antihistamines (eg, famotidine or ranitidine), meperidine, or ibuprofen to the mandatory premedication. Prophylactic steroids are NOT permitted.

5.3.7.3.2. Management of Investigational Product-related Severe Hypersensitivity Reactions and Flu-like Symptoms

Many mAb therapies can induce flu-like symptoms and hypersensitivity reactions, including impaired airway, decreased oxygen saturation (<92%), confusion, lethargy, hypotension, pale/clammy skin, and cyanosis. In addition, given the CMP-001 mechanism of action resulting in secretion of large amounts of type 1 interferons, flu-like symptoms similar to that seen after administration of interferons (eg, fever, rigors, nausea, and vomiting) may be associated with IT injection of CMP-001.

Investigational products (mAbs) should be administered in a setting that allows for immediate access to an intensive care unit or equivalent environment if required. Patient should be placed on monitor immediately and epinephrine injection and dexamethasone infusion should be available for immediate access.

For prophylaxis of flu-like symptoms, and for patients treated with CMP-001, 25 mg indomethacin or comparable nonsteroidal anti- inflammatory drugs (NSAID) dose (eg, ibuprofen 600 mg, naproxen sodium 500 mg) may be administered at Investigator discretion 2 hours before and 8 hours after the start of each dose of investigational product(s) thought to be related to symptoms. Alternative treatments for fever (eg, paracetamol or ibuprofen) and rigors (eg, meperidine) may be given to patients at the discretion of the Investigator.

[figure not shown]
5.3.7.3.3. Management of Symptoms Associated with Cytokine Release

CMP-001 is designed to specifically bind to TLR9 expressed in the endosomes of pDCs. Upon activation through TLR9, pDCs will secrete large amounts of type 1 interferons and associated Th1-promoting cytokines. Therefore it is expected that symptoms associated with IFN-inducible chemokines and cytokines release, such as chills/rigors, fever, nausea/vomiting and hypotension, may occur within hours of a CMP-001 IT injection.

The recommended algorithm for the treatment of symptoms associated with cytokine release below has been adapted for the treatment of CRS resulting from other immunotherapies such as CAR-T cell therapy.¹⁰¹ Its effectiveness in treating symptoms associated with cytokine release resulting from CMP-001 has not been previously studied. The first line of treatment for hypotension unresponsive to supportive care such as fluids, is stress dose steroids as outlined below. Additional treatment measures include the use of drugs targeting specific cytokines believed to be involved in the development of CRS-induced hypotension.

Figure 22 Recommended Treatment Algorithm for Cytokine Release Symptoms

Recommended Treatment algorithm for Cytokine-Release Symptoms^a

IV=intravenously; NSAIDs=non-steroidal anti-inflammatory drugs; po=per os (orally); Q8=every 8 hours.

a. Lee et al.¹⁰¹

b. ACTEMRA US Prescribing Information.¹⁰²

Table 23. Cytokine Release Syndrome Revised Grading system

Grade	Toxicity
Grade 1	Symptoms are not life threatening and require symptomatic treatment only, eg, fever, nausea, fatigue, headache, myalgias, malaise
Grade 2	Symptoms require and respond to moderate intervention Oxygen requirement <40% or Hypotension responsive to fluids or low dose of one vasopressor or Grade 2 organ toxicity
Grade 3	Symptoms require and respond to aggressive intervention Oxygen requirement $\geq 40\%$ or Hypotension requiring high dose* or multiple vasopressors or Grade 3 organ toxicity or Grade 4 transaminitis
Grade 4	Life-threatening symptoms Requirement for ventilator support or Grade 4 organ toxicity (excluding transaminitis)
Grade 5	Death

Table 24. High-Dose Vasopressors (All Doses Are Required for ≥ 3 hours)

Pressor	Dose
Norepinephrine monotherapy	$\geq 20 \mu\text{g}/\text{min}$
Dopamine monotherapy	$\geq 10 \mu\text{g}/\text{kg}/\text{min}$
Phenylephrine monotherapy	$\geq 200 \mu\text{g}/\text{min}$
Epinephrine monotherapy	$\geq 10 \mu\text{g}/\text{min}$
If on vasopressin	Vasopressin + norepinephrine equivalent of $\geq 10 \mu\text{g}/\text{min}^*$
If on combination vasopressors (not vasopressin)	Norepinephrine equivalent of $\geq 20 \mu\text{g}/\text{min}^*$

*VASST Trial vasopressor equivalent equation: norepinephrine equivalent dose = [norepinephrine ($\mu\text{g}/\text{min}$)] + [dopamine ($\mu\text{g}/\text{kg}/\text{min}$) $\div 2$] + [epinephrine ($\mu\text{g}/\text{min}$)] + [phenylephrine ($\mu\text{g}/\text{min}$) $\div 10$].

Adapted from Lee et al.¹⁰¹

5.3.7.3.4. Management of Injection Site-Reactions

If a patient develops inflammation at the injection site, this may be managed using cold compresses and/or acetaminophen or NSAIDs.

5.3.7.3.5. Management of Immune-Related Adverse Events

Treatment of irAEs is mainly dependent upon severity (NCI CTCAE grade v.4.03):

- Grade 1 or 2: treat symptomatically or with moderate-dose steroids, more frequent monitoring;
- Grade 1 or 2 (persistent): manage similar to Grade 3 to 4 AE;
- Grade 3 or 4: treat with high-dose corticosteroids.

Management of irAEs for utomilumab, PF-04518600, and PD 0360324, is consistent with the management of irAEs for avelumab. Treatment of irAEs should follow guidelines set forth in [Table 25](#).

Table 25. Management of Immune-Related Adverse Events

Gastrointestinal irAEs		
Diarrhea / Colitis (NCI CTCAE v4)	Initial Management	Follow-up Management
Grade 1 Diarrhea: <4 stools/day over baseline; Colitis: asymptomatic	Continue investigational product therapy. Symptomatic treatment (eg, loperamide).	Close monitoring for worsening symptoms. Educate patient to report worsening immediately. If worsens: Treat as Grade 2 or ¾.
Grade 2 Diarrhea: 4 to 6 stools per day over baseline; IV fluids indicated <24 hours; not interfering with ADL Colitis: abdominal pain; blood in stool	Withhold investigational product therapy. Symptomatic treatment.	If improves to Grade 1: Resume investigational product therapy. If persists >5-7 days or recur: Treat as Grade 3 to 4.
Grade 3 to 4 Diarrhea (Grade 3): ≥7 stools per day over baseline; incontinence; IV fluids ≥24 hrs.; interfering with ADL Colitis (Grade 3): severe abdominal pain, medical intervention indicated, peritoneal signs Grade 4: life-threatening, perforation	Withhold investigational product for Grade 3. Permanently discontinue investigational product for Grade 4 or recurrent Grade 3. 1.0 to 2.0 mg/kg/day prednisone or equivalent. Add prophylactic antibiotics for opportunistic infections. Consider lower endoscopy.	If improves: Continue steroids until Grade ≤1, then taper over at least 1 month; resume investigational product following steroids taper (for initial Grade 3). If persists >3 to 5 days, or recur after improvement: Add infliximab 5 mg/kg (if no contraindication). Note: Infliximab should not be used in cases of perforation or sepsis.
Dermatological irAEs		
Rash (NCI-CTCAE v4)	Initial Management	Follow-up Management
Grade 1 to 2 Covering ≤30% body surface area	Symptomatic therapy (eg, antihistamines, topical steroids). Continue investigational product therapy.	If Grade 2 persists >1 to 2 weeks or recurs: Consider skin biopsy. Withhold investigational product therapy. Consider 0.5 to 1.0 mg/kg/day prednisone or equivalent. Once improving, taper steroids over at least 1 month, consider prophylactic antibiotics for opportunistic infections, and resume investigational product therapy following steroids taper. If worsens:

Table 25. Management of Immune-Related Adverse Events

		Treat as Grade 3 to 4.
Grade 3 to 4 Covering >30% body surface area; life threatening consequences	Withhold investigational product for Grade 3. Permanently discontinue for Grade 4 or recurrent Grade 3. Consider skin biopsy. Dermatology consult. 1.0 to 2.0 mg/kg/day prednisone or equivalent. Add prophylactic antibiotics for opportunistic infections.	If improves to Grade \leq 1: Taper steroids over at least 1 month. Resume investigational product therapy following steroids taper (for initial Grade 3).
Pulmonary irAEs		
Grade of Pneumonitis (NCI-CTCAE v4)	Initial Management	Follow-up Management
Grade 1 Radiographic changes only	Consider withholding of investigational product therapy. Monitor for symptoms every 2 to 3 days. Consider Pulmonary and Infectious Disease consults.	Re-assess at least every 3 weeks. If worsens: Treat as Grade 2 or Grade 3 to 4.
Grade 2 Mild to moderate new symptoms	Withhold investigational product therapy. Pulmonary and Infectious Disease consults. Monitor symptoms daily, consider hospitalization. 1.0 to 2.0 mg/kg/day prednisone or equivalent. Add prophylactic antibiotics for opportunistic infections. Consider bronchoscopy, lung	Re-assess every 1 to 3 days. If improves: When symptoms return to near baseline, taper steroids over at least 1 month. Resume investigational product therapy. If not improving after 2 weeks or worsening or for recurrent Grade 2: Treat as Grade 3 to 4.

Table 25. Management of Immune-Related Adverse Events

	biopsy	
Grade 3 to 4 Severe new symptoms; New/worsening hypoxia; life-threatening	Permanently discontinue investigational product therapy. Hospitalize. Pulmonary and Infectious Disease consults. 1.0 to 2.0 mg/kg/day prednisone or equivalent. Add prophylactic antibiotics for opportunistic infections. Consider bronchoscopy, lung biopsy.	If improves to baseline: Taper steroids over at least 6 weeks. If not improving after 48 hours or worsening: Add additional immunosuppression (eg, infliximab, cyclophosphamide, intravenous immunoglobulin, or mycophenolate mofetil).
Hepatic irAEs		
Liver Function Tests (LFT) Increase (NCI-CTCAE v4)	Initial Management	Follow-up Management
Grade 1 Grade 1 AST or ALT > ULN to 3.0 x ULN and/or Total bilirubin > ULN to 1.5 x ULN	Continue investigational product therapy.	Continue liver function monitoring. If worsens: Treat as Grade 2 or 3 to 4.
Grade 2 AST or ALT >3.0 to \leq 5 x ULN and/or total bilirubin >1.5 to \leq 3 x ULN	Withhold investigational product therapy. Increase frequency of monitoring to every 3 days.	If returns to baseline: Resume routine monitoring, resume investigational product therapy. If elevations persist >5 to 7 days or worsen: Treat as Grade 3 or Grade 4.
Grade 3 to 4 AST or ALT >5 x ULN and /or total bilirubin >3 x ULN	Permanently discontinue investigational product therapy. Increase frequency of monitoring to every 1 to 2 days. 1.0 to 2.0 mg/kg/day prednisone or equivalent. Add prophylactic antibiotics for opportunistic infections. Consult gastroenterologist/hepatologist. Consider obtaining MRI/CT scan of liver and liver biopsy if clinically warranted.	If returns to Grade \leq 1: Taper steroids over at least 1 month. If does not improve in >3 to 5 days, worsens or rebounds: Add mycophenolate mofetil 1 gram (g) twice daily. If no response within an additional 3 to 5 days, consider other immunosuppressants per local guidelines.

Table 25. Management of Immune-Related Adverse Events

Renal irAEs		
Grade of Creatinine Increased (NCI-CTCAE v4)	Initial Management	Follow-up Management
Grade 1 Creatinine increased > ULN–1.5 x ULN	Continue investigational product therapy.	Continue renal function monitoring. If worsens: Treat as Grade 2 to 3 or 4.
Grade 2 to 3 Creatinine increased > 1.5 – 6 x ULN	Withhold investigational product therapy. Increase frequency of monitoring to every 3 days. 1.0 to 2.0 mg/kg/day prednisone or equivalent. Add prophylactic antibiotics for opportunistic infections. Consider renal biopsy.	If returns to Grade \leq 1: Taper steroids over at least 1 month and resume investigational product therapy following steroids taper. If worsens: Treat as Grade 4.
Grade 4 Creatinine increased > 6 x ULN	Permanently discontinue investigational product therapy. Monitor creatinine daily. 1.0 to 2.0 mg/kg/day prednisone or equivalent. Add prophylactic antibiotics for opportunistic infections. Consider renal biopsy. Nephrology consult.	If returns to Grade \leq 1: Taper steroids over at least 1 month.
Cardiac irAEs		
Myocarditis	Initial Management	Follow-up Management
New onset of cardiac signs or symptoms and / or new laboratory cardiac biomarker elevations (eg, troponin, CK-MB, BNP) or cardiac imaging abnormalities suggestive of myocarditis.	Withhold investigational product therapy. Hospitalize. In the presence of life threatening cardiac decompensation, consider transfer to a facility experienced in advanced heart failure and arrhythmia management. Cardiology consult to establish etiology and rule-out immune-related myocarditis.	If symptoms improve and immune-related etiology is ruled out, re-start investigational product therapy. If symptoms do not improve/worsen, viral myocarditis is excluded, and immune-related etiology is suspected or confirmed following cardiology consult, manage as immune-related myocarditis

Table 25. Management of Immune-Related Adverse Events

	Guideline based supportive treatment as per cardiology consult.* Consider myocardial biopsy if recommended per cardiology consult.	
Immune-related myocarditis	Permanently discontinue investigational product therapy. Guideline based supportive treatment as appropriate as per cardiology consult.* 1.0 to 2.0 mg/kg/day prednisone or equivalent.	Once improving, taper steroids over at least 1 month and add prophylactic antibiotics for opportunistic infections. If no improvement or worsening, consider additional immunosuppressants (eg, azathioprine, cyclosporine A).

*Local guidelines, or eg, European Society of Cardiology or American Heart Association guidelines.

European Society of Cardiology guidelines website:
<https://www.escardio.org/Guidelines/Clinical-Practice-Guidelines>

American Heart Association guidelines website:
<http://professional.heart.org/professional/GuidelinesStatements/searchresults.jsp?q=&y=&t=1001>

Endocrine irAEs

Endocrine Disorder	Management	Follow-up
Grade 1 or Grade 2 endocrinopathies (hypothyroidism, hyperthyroidism, adrenal insufficiency, type I diabetes mellitus)	
Continue investigational product therapy.
 
Endocrinology consult if needed.
 
Start thyroid hormone replacement therapy (for hypothyroidism), anti-thyroid treatment (for hyperthyroidism), corticosteroids (for adrenal insufficiency), or insulin (for type I diabetes mellitus) as appropriate.
 
Rule-out secondary endocrinopathies (eg, hypopituitarism/hypophysitis).
	Continue hormone replacement/suppression and monitoring of endocrine function as appropriate.
Grade 3 or Grade 4 endocrinopathies (hypothyroidism, hyperthyroidism, adrenal insufficiency, type I diabetes mellitus)	
Withhold investigational product therapy.
 
Consider hospitalization.
 
Endocrinology consult.
 
Start thyroid hormone replacement therapy (for hypothyroidism), anti-thyroid treatment (for
	
Resume investigational product once symptoms and/or laboratory tests improve to Grade ≤ 1 (with or without hormone replacement/suppression).
 
Continue hormone replacement/ suppression and monitoring of endocrine function as appropriate.

Table 25. Management of Immune-Related Adverse Events

	
hyperthyroidism), corticosteroids (for adrenal insufficiency), or insulin (for type I diabetes mellitus) as appropriate.
 
Rule-out secondary endocrinopathies (eg, hypopituitarism/hypophysitis).
	
Hypopituitarism/Hypophysitis (secondary endocrinopathies)	
If secondary thyroid and/or adrenal insufficiency is confirmed (eg, subnormal serum thyroxine with inappropriately low thyroid-stimulating hormone and/or low serum cortisol with inappropriately low adrenocorticotrophic hormone):
 
 Refer to endocrinologist for dynamic testing as indicated and measurement of other hormones (FSH, LH, GH/IGF-1, PRL, testosterone in men, estrogens in women). Hormone replacement/ suppressive therapy as appropriate. Perform pituitary MRI and visual field examination as indicated. 
If hypophysitis confirmed:
 
 Continue investigational product if mild or moderate symptoms with normal MRI. Repeat the MRI in 1 month. Withhold investigational product if severe symptoms or life-threatening symptoms of hypophysitis and/or abnormal MRI. Consider hospitalization. Initiate high-dose corticosteroids (1 to 2 mg/kg/day methylprednisolone IV or equivalent) followed by corticosteroids taper during at least 1 month. Add prophylactic antibiotics for opportunistic infections. 	
Resume investigational product once symptoms and hormone tests improve (with or without hormone replacement).
 
In addition, for hypophysitis with abnormal MRI, resume investigational product only once shrinkage of the pituitary gland on MRI scan is documented.
 
Continue hormone replacement/ suppression therapy as appropriate.

Table 25. Management of Immune-Related Adverse Events

Other irAEs (not described above)		
Grade of other irAEs (NCI-CTCAE v4)	Initial Management	Follow-up Management
Grade 2 or Grade 3 clinical signs or symptoms suggestive of a potential irAE	Withhold investigational product therapy pending clinical investigation.	If irAE is ruled out, manage as appropriate according to the diagnosis and consider resuming investigational product therapy. If irAE is confirmed, treated as Grade 2 or 3 irAE.
Grade 2 irAE or first occurrence of Grade 3 irAE	Withhold investigational product therapy. 1.0 to 2.0 mg/kg/day prednisone or equivalent. Add prophylactic antibiotics for opportunistic infections. Specialty consult as appropriate.	If improves to Grade ≤ 1 : Taper steroids over at least 1 month and resume investigational product therapy following steroids taper.
Recurrence of same Grade 3 irAE	Permanently discontinue investigational product therapy. 1.0 to 2.0 mg/kg/day prednisone or equivalent. Add prophylactic antibiotics for opportunistic infections. Specialty consult as appropriate.	If improves to Grade ≤ 1 : Taper steroids over at least 1 month.
Grade 4 irAE	Permanently discontinue investigational product therapy. 1.0 to 2.0 mg/kg/day prednisone or equivalent and/or other immunosuppressants as needed. Add prophylactic antibiotics for opportunistic infections. Specialty consult.	If improves to Grade ≤ 1 : Taper steroids over at least 1 month.
Requirement for ≥ 10 mg prednisone per day or equivalent for more than 12 weeks for reasons other than hormonal replacement for adrenal insufficiency Persistent Grade 2 or 3 irAE lasting ≥ 12 weeks	Permanently discontinue investigational product therapy. Specialty consult as appropriate.	

ALT=alanine aminotransferase, AST=aspartate aminotransferase, irAE=immune-related adverse event, IV=intravenous, MRI=magnetic resonance imaging, NCI-CTCAE=National Cancer Institute-Common Terminology Criteria for Adverse Events, TSH=thyroid-stimulating hormone, ULN=upper limit of normal.

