- Patient must not have received previous OX-40 agonists or 4-1BB agonists or IT anticancer treatment including, talimogene laherparepvec, other oncolytic virus therapies, or other TLR agonists.

2. Age ≥ 18 years (≥ 20 years where applicable according to local regulation).
3. Eastern Cooperative Oncology Group (ECOG) Performance Status (PS) 0 or 1.
4. Estimated life expectancy of at least 3 months.
5. Adequate bone marrow function, defined as:
 - a. ANC $\geq 1.5 \times 10^9/L$ ($\geq 1,500/\mu L$);
 - b. Platelets $\geq 100 \times 10^9/L$ ($\geq 100,000/\mu L$);
 - c. Hemoglobin ≥ 9 g/dL (>5.6 mmol/L).

Patients must be transfusion independent (ie, no blood product transfusions for a period of at least 14 days prior to study entry).

6. Adequate renal function, including estimated creatinine clearance ≥ 50 mL/min (Phase 1b) or ≥ 30 mL/min (Phase 2) as calculated using the Cockcroft-Gault (CG) equation.
7. Adequate liver function, including:
 - a. Total serum bilirubin $\leq 1.5 \times$ ULN unless the patient has documented Gilbert syndrome;
 - b. AST and ALT $\leq 2.5 \times$ ULN.
8. Resolved acute effects of any prior therapy to baseline severity or NCI CTCAE v.4.03 Grade ≤ 1 (except alopecia and Grade ≤ 2 sensory neuropathy are acceptable).
9. Negative serum/urine pregnancy test (for females of childbearing potential) at screening.
10. Sexually active male patients able to father children and female patients of childbearing potential and at risk for pregnancy must agree to use at least one highly effective method of contraception as detailed in [Section 4.3](#), throughout the study and for at least 90 days after the last dose of assigned treatment or longer as required by local regulations.

Female patients who are not of childbearing potential (ie, meet at least one of the following criteria):

- Have undergone a documented hysterectomy and/or bilateral oophorectomy;
- Have medically confirmed ovarian failure; or
- Achieved postmenopausal status, defined as follows: cessation of regular menses for at least 12 consecutive months with no alternative pathological or physiological cause; status may be confirmed by having a serum follicle-stimulating hormone (FSH) level within the laboratory's reference range for postmenopausal women.

11. Evidence of a personally signed and dated informed consent document indicating that the patient has been informed of all pertinent aspects of the study.

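### A Phase 2 patient admitted near the 30 mL/min clearance floor can recover fully from a renal immune-related event and still not meet Table 25's condition for steroid taper and restart

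*Protocol*

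**What the plan says.** Section 4.1, criterion 6, is the only renal inclusion criterion. Its Phase 2 floor is "30 mL/min (Phase 2) as calculated using the Cockcroft-Gault (CG) equation"; the Phase 1b floor is 50 mL/min. No serum creatinine limit is given for either phase.

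Table 25 in Section 5.3.7.3.5 sets out the renal rows:

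- The lowest band is "Grade 1 Creatinine increased > ULN–1.5 x ULN", and study drug continues.
- The next is "Grade 2 to 3 Creatinine increased > 1.5 – 6 x ULN". Study drug is withheld and prednisone 1.0 to 2.0 mg/kg/day (or equivalent) is given. On return to Grade 1 or better the instruction is "Taper steroids over at least 1 month and resume investigational product therapy following steroids taper".
- Grade 4 (above 6 x ULN) means permanent discontinuation with the same steroid range. Taper again depends on return to Grade 1 or better.

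None of the renal rows mentions the patient's own baseline. The hepatic Grade 2 row of the same table does: "If returns to baseline: Resume routine monitoring, resume investigational product therapy".

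The last part of Table 25, for immune-related events that the table has not already described, requires permanent discontinuation for "Requirement for ≥ 10 mg prednisone per day or equivalent for more than 12 weeks" or for a Grade 2 or 3 event that persists for 12 weeks or more.

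**The concern.** Eligibility is set on clearance, which depends on age, weight and sex as well as creatinine. Recovery is set on creatinine relative to ULN. Nothing ties the two scales together, so a value that the protocol accepts at entry can lie above the value that it demands as proof of recovery.

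A patient in that position who has a renal immune-related event and returns completely to the entry value would still read as Grade 2 to 3. Followed literally, the table then gives no point at which to taper the steroid and, for a Grade 2 to 3 event, none at which to restart study drug. That is first a patient-safety matter. It also touches the data: exposure, time off treatment and the recorded course of the event would reflect a mismatch of reference values and not continuing toxicity.

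**Working it through.** The protocol states no figure here to reproduce. The check is whether a patient can satisfy criterion 6 and have an entry creatinine above 1.5 x ULN.

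**Inputs from the protocol:** clearance floors of 30 mL/min (Phase 2) and 50 mL/min (Phase 1b), by Cockcroft-Gault; recovery limit of 1.5 x ULN.

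**Assumptions:** the usual Cockcroft-Gault constants (the protocol names the equation but does not print it); ages and weights as shown; ULN 1.2 to 1.4 mg/dL for men and 1.0 to 1.2 mg/dL for women.

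**Formula, solved for creatinine:** creatinine = (140 − age) x weight x (0.85 if female) / (72 x clearance), then divided by ULN.

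**At 30 mL/min** (72 x 30 = 2160):

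| Patient | Creatinine, mg/dL | Multiple of ULN (low / mid / high ULN) |
|---|---|---|
| Man, 65 y, 70 kg | 75 x 70 / 2160 = 2.43 | 2.03 / 1.87 / 1.74 |
| Man, 60 y, 80 kg | 80 x 80 / 2160 = 2.96 | 2.47 / 2.28 / 2.12 |
| Woman, 65 y, 70 kg | 75 x 70 x 0.85 / 2160 = 2.07 | 2.07 / 1.88 / 1.72 |
| Woman, 65 y, 60 kg | 75 x 60 x 0.85 / 2160 = 1.77 | 1.77 / 1.61 / 1.48 |
| Man, 80 y, 60 kg | 60 x 60 / 2160 = 1.67 | 1.39 / 1.28 / 1.19 |
| Woman, 75 y, 50 kg | 65 x 50 x 0.85 / 2160 = 1.28 | 1.28 / 1.16 / 1.07 |

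The first three exceed 1.5 x ULN throughout the assumed range. The fourth does so except at the highest ULN. The last two do not. At age 65 and 30 mL/min, entry creatinine passes 1.5 x ULN above about 52 to 61 kg in men (1.5 x 1.2 x 2160 / 75 = 51.8; with ULN 1.4, 60.5) and about 51 to 61 kg in women.

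**Width of the overlap.** For a 65-year-old, 75 kg man, 1.5 x ULN corresponds to a clearance of 75 x 75 / (72 x 1.8) = 43.4 mL/min at ULN 1.2, and 75 x 75 / (72 x 2.1) = 37.2 at ULN 1.4. Between 30 mL/min and that value he is eligible for Phase 2 and above the recovery limit.

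**At 50 mL/min** (72 x 50 = 3600): the 65-year-old, 70 kg man is at 5250 / 3600 = 1.46 mg/dL, or 1.22 / 1.12 / 1.04 x ULN, and is clear of the overlap. A 50-year-old, 90 kg man is at 8100 / 3600 = 2.25 mg/dL, or 1.88 / 1.73 / 1.61 x ULN, and is not. The overlap narrows at the Phase 1b floor but does not vanish.

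**Other limits on entry creatinine.** Exclusion 20 concerns toxicity from prior therapy and unresolved or recent immune-related events, and tolerates some Grade 2 events on investigator judgment. Exclusion 21 is investigator judgment with no number. Neither closes the gap.

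**Comparison with the liver.** Entry limits are AST and ALT at most 2.5 x ULN and bilirubin at most 1.5 x ULN (Gilbert syndrome excepted). Hepatic Grade 1 runs to 3.0 x ULN for the enzymes and 1.5 x ULN for bilirubin. A patient back at an accepted entry value is therefore at Grade 1 or better, Gilbert syndrome apart. The renal criterion has no such alignment.

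**The case against.** The strongest reply is that the two passages can both be followed for nearly everyone, and much of it stands.

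- A reader might infer that affected patients are in the hold band from day one. They are not. Table 25 governs immune-related events, and the Schedule of Activities footnotes on baseline signs and symptoms direct that only new or worsening conditions be reported as adverse events. A stable entry creatinine triggers nothing.
- A reader might infer that such a patient can never restart. The condition is out of reach only while creatinine stays above 1.5 x ULN; an improvement on the entry value to that level or below would satisfy it.
- A reader might infer prolonged high-dose prednisone followed by a forced stop at 12 weeks. The 12-week rules sit under events not described earlier in the table, and renal events are described earlier, so it is unclear whether they apply. Sections 5.3.7.3 and 5.3.7.3.5 present the irAE measures as recommendations and guidelines, and Section 5.6 leaves the final decision on supportive therapy to the investigator or primary physician.
- A reader might take the hepatic Grade 2 row as proof that the renal rows break the table's convention. They do not. Hepatic Grade 3 to 4, skin Grade 3 to 4 and other immune-related events also use Grade 1 or better, and the hepatic Grade 2 row carries no steroid.
- The scope is limited. Further enrolment in Combinations A and B, and Phase 2 of C and D, are not planned. That leaves Combination F Phase 2, with up to 14 additional patients per cohort.

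These points narrow the finding but do not remove it. The renal rows still state one condition for taper and restart, and a patient fully back at an accepted baseline can fail it.

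**Conclusion.** The point holds in a limited form: criterion 6 and the renal rows of Table 25 do not fit together for some eligible Phase 2 patients near the clearance floor. In the examples that overlap, entry creatinine at 30 mL/min is roughly 1.6 to 2.5 x ULN against a recovery limit of 1.5, leaving aside the lighter woman at the highest assumed ULN (1.48).

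The failure needs a sequence of events: entry above 1.5 x ULN, then a renal immune-related event, then resolution to baseline. How many patients would meet it cannot be derived from the protocol, and no effect on response or exposure estimates can be quantified. The sizes rest on assumed ages, weights, ULN values and Cockcroft-Gault constants, but the existence of the overlap holds across the whole ULN range used.

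This is more than an omitted detail, because the stated rule, followed as printed, gives the wrong answer for a recovered patient. It should be corrected while Combination F Phase 2 is still governed by it.

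**What to change.** Reconcile criterion 6 in Section 4.1 with the renal rows of Table 25, so that a patient who is back at a creatinine accepted at entry can meet the printed condition for taper (all renal rows with steroids) and for restart (Grade 2 to 3). State explicitly whether recovery is judged against baseline or ULN, and whether the 12-week permanent-stop rules apply to renal events. Check at the same time that the Phase 1b floor of 50 mL/min is covered. Which limit or reference to use is for the sponsor's clinicians; none is proposed here.

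The cost is a wording change in an amendment. No new assessments are needed, since creatinine is already part of the screening and on-treatment chemistry panel (Table 26).
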